14.3 Pregnancy

WOCBP (see [Section 5.1](#) for definition) must have a negative UPT prior to study enrollment and must use a highly effective method of birth control during the course of the study, in a manner such that risk of failure is minimized. Prior to study enrollment, WOCBP must be advised of the importance of avoiding pregnancy during trial participation and the potential risk factors for an unintentional pregnancy. The subject and parent/guardian must sign an informed consent/assent form documenting this discussion.

During the study, all WOCBP should be instructed to contact the investigator immediately if they suspect they might be pregnant (e.g., missed or late menstrual period).

WOCBP enrolling into the study must have a pregnancy test prior to study therapy, and at EOS. The study therapy must be withheld until the results of laboratory pregnancy testing are known, and a negative UPT must be confirmed to continue in the trial. If pregnancy is confirmed during screening, the subject must not receive test article and must not be enrolled in the study.

If a subject or investigator suspects that a subject may be pregnant at any time during the study, the test article must be withheld until the results of laboratory pregnancy testing are available. If pregnancy is confirmed, the subject must not apply further test article and must be discontinued from the study.

If following initiation of study treatment, it is subsequently discovered that a trial subject was pregnant or may have been pregnant at the time of test article exposure, the investigator must immediately notify the Medical Monitor of this event, and record the pregnancy on the appropriate pregnancy surveillance form. The form will be sent to the CRO. The

investigator must notify the IRB of any pregnancy associated with the study therapy and keep careful source documentation of the event.

Protocol-required procedures for those subjects that are discontinued from the study must be performed on the subject unless contraindicated by pregnancy (e.g., x-ray studies). Other appropriate pregnancy follow-up procedures should be considered if indicated, including counseling of the subject by the investigator and her managing physician or health care provider (e.g., obstetrician). In addition, the investigator must report to the CRO, on the appropriate CRO pregnancy surveillance form(s), any follow-up information regarding the course of the pregnancy, including perinatal and neonatal outcome. Although pregnancy itself is not an AE, any complications during pregnancy should be recorded as AEs (or SAEs, if they fulfill the SAE criteria). Abortion, whether accidental, therapeutic, or spontaneous should be reported as an SAE. Offspring should be followed for a minimum of eight weeks. Any congenital anomaly/birth defect in a child born to a subject exposed to the test article(s) should be recorded as an SAE and details documented in the pregnancy surveillance form.

15. BLINDING/UNBLINDING

This study is an open label study. There is no blinding of the test article.

16. CLINICAL SUPPLIES

16.1 Test Article Information

Test articles will be packaged and labeled by the Sponsor or designee. Detailed information on the packaging/labeling, storage and preparation, dispensing, accountability etc. is included in [Appendix 2](#).

16.2 Supplies Provided by CRO

- EDC (e.g. access to e-CRFs, etc.)
- Subject Diaries
- Source document draft templates
- Site regulatory binder
- UPT kits
- Weighing scales (if necessary)
- Medications for Additional Acne Management: OTC acne cleanser containing 2% salicylic acid or 5% benzoyl peroxide and doxycycline (for US sites only)

16.3 Supplies Provided by Investigator

- Urine collection containers for UPTs

17. STATISTICAL CONSIDERATIONS

17.1 Sample Size

For large samples, the two-sided confidence interval for a single proportion extends a distance $\omega = z_{1-\frac{\alpha}{2}} \sqrt{\frac{\pi(1-\pi)}{n}}$ from the observed proportion in both directions. An incidence no greater than 1% of important AEs out of 100 subjects will provide the estimate of no greater than a 3% prevalence of important AEs at the 95% confidence level with a much larger number of subjects exposed for the same duration (i.e., 12 months). Applying the same approach, an incidence no greater than 1% of important AEs out of 300 subjects will provide the estimate of no greater than a 2.1% prevalence of important AEs at the 95% confidence level with a much larger number of subjects exposed for the same duration (i.e., 6 months).

Approximately six hundred (600) subjects will be enrolled in order to have 300 subjects on-study at 6 months and 100 subjects on-study at 12 months. These treatment durations include the 0 or 3 months of active treatment in the Phase 3 pivotal studies (CB-03-01/25 and CB-03-01/26).

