### 6.2 Hypothesis Tests

No formal hypothesis test will be performed.

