### 6.3 Sample Size Calculations

For large samples, the two-sided confidence interval for a single proportion extends a distance

$$\omega = z_{1-\frac{\alpha}{2}} \sqrt{\frac{\pi(1-\pi)}{n}}$$

from the observed proportion in both directions.

An incidence no greater than 1% of important AEs out of 100 subjects will provide the estimate of no greater than a 3% prevalence of important AEs at the 95% confidence level with a much larger number of subjects exposed for the same duration (i.e., 12 months). Applying the same approach, an incidence no greater than 1% of important AEs out of 300 subjects will provide the estimate of no greater than a 2.1% prevalence of important AEs at the 95% confidence level with a much larger number of subjects exposed for the same duration (i.e., 6 months).

Approximately six hundred (600) subjects had to be enrolled in order to have 300 subjects on-study at 6 months and 100 subjects on-study at 12 months. These treatment durations include the 0 or 3 months of active treatment in the Phase 3 pivotal studies (CB-03-01/25 and CB-03-01/26).

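### The 3% and 2.1% upper limits behind the 100- and 300-subject targets use a large-sample interval at 1 and 3 events; exact limits are 5.4% and 2.9%

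*Protocol*

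**What the plan says.** Protocol 17.1 introduces its formula with the words "For large samples, the two-sided confidence interval for a single proportion extends a distance" and gives the half-width as z times the square root of π(1−π)/n. It then states, for 12 months of exposure, "An incidence no greater than 1% of important AEs out of 100 subjects will provide the estimate of no greater than a 3% prevalence", at the 95% confidence level. For 6 months it uses the same method ("Applying the same approach"), and SAP 6.3 repeats the result: "an incidence no greater than 1% of important AEs out of 300 subjects will provide the estimate of no greater than a 2.1% prevalence". The protocol synopsis carries the same text.

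These limits support the enrolment plan, in which about 600 "subjects will be enrolled in order to have 300 subjects on-study at 6 months and 100 subjects on-study at 12 months". There is no power calculation, because SAP 6.2 says "No formal hypothesis test will be performed". No other interval method is named in either document. SAP 7.1 mentions confidence limits only in a rounding rule.

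**The concern.** An observed 1% is 1 event among 100 subjects or 3 among 300. The Wald interval relies on a normal approximation to the binomial, which fails at counts this small. It also builds its width from the observed proportion, so a low count makes the estimate look more precise than it is. The protocol's own introduction to the formula restricts it to large samples.

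Long-term safety is the primary objective and no hypothesis is tested. The two limits are therefore the only quantitative statement of what the trial can rule out. If they are too low, a reader is told that 1 event in 100 at 12 months bounds the important-AE rate at 3% when appreciably higher rates remain compatible with that result. The error favours the product.

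**Working it through.** **Inputs** (Protocol 17.1, repeated in SAP 6.3): two-sided interval, 95% confidence (z = 1.96), observed proportion p = 0.01, n = 100 (x = 1 event) and n = 300 (x = 3 events).

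**1. Reproducing the plan's figures.** Wald limits: p ± 1.96 × √(p(1−p)/n).

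- n = 100: 0.01 ± 1.96 × √(0.0099/100) = 0.01 ± 0.0195, giving −0.95% to 2.95% (stated: 3%).
- n = 300: 0.01 ± 1.96 × √(0.0099/300) = 0.01 ± 0.0113, giving −0.13% to 2.13% (stated: 2.1%).

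Both stated figures are recovered, so there is no slip in the arithmetic. The negative lower limits show that the approximation has broken down. At 0 events, which an incidence of at most 1% includes, the formula gives an interval of zero width.

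**2. Exact limits.** The Clopper-Pearson upper limit p_U solves P(X ≤ x | n, p_U) = 0.025. It is the 0.975 quantile of a Beta(x+1, n−x) distribution.

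- 1/100: Beta(2, 99) gives 5.446%, that is 5.45% (5.4% to one decimal). The lower limit is 0.03%.
- 3/300: Beta(4, 297) gives 2.894%, that is 2.89% (2.9% to one decimal). The lower limit is 0.21%.

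The ratios to the stated limits are 5.45/3 ≈ 1.8 and 2.89/2.1 ≈ 1.4.

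**3. Does the result depend on choosing Clopper-Pearson?** Upper 95% limits by method:

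| Method | 1/100 | 3/300 |
|---|---|---|
| Stated in the plan | 3% | 2.1% |
| Wald, two-sided | 2.95% | 2.13% |
| Clopper-Pearson, two-sided | 5.45% | 2.89% |
| Wilson, two-sided | 5.45% | 2.90% |
| Mid-P, two-sided | 4.83% | 2.70% |
| Jeffreys, two-sided | 4.58% | 2.64% |
| Exact, one-sided | 4.66% | 2.56% |

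Every small-count method in the table, including the one-sided exact limit, lies above the stated figures.

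**4. Direct check of the confidence claimed.** If a stated limit were a valid two-sided 95% upper limit, a true rate equal to it would give a count this low with probability 2.5%.

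- True rate 3%, n = 100: P(X ≤ 1) = 0.97^100 + 100 × 0.03 × 0.97^99 = 19.5%.
- True rate 2.1%, n = 300: P(X ≤ 3) = 12.4%.
- True rate 5%, n = 100: P(X ≤ 1) = 3.7%. True rate 2.8%, n = 300: P(X ≤ 3) = 3.1%. Both exceed 2.5%, so a two-sided 95% exact interval does not exclude these rates either.

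**5. Coverage.** Summing over all possible counts at a true rate of 1%, the nominal 95% Wald interval covers the truth 63% of the time with n = 100 and 80% with n = 300.

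**The case against.** The strongest reply is that nothing in the trial depends on these limits. The study is descriptive, with no test, no interim analysis and no success criterion tied to 3% or 2.1%. The planned AE output is counts and percentages. SAP 2.5 reports 609 subjects already included, so amending the protocol cannot change recruitment. All of this is true, and it confines the damage to the precision statement. It does not make that statement correct. The documents chose to attach 95% confidence bounds to their targets, and the bounds do not have that confidence.

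Other points stand in part:

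- The fault is the choice of approximation, not the arithmetic.
- The plan's claim is directional, so a one-sided reading is arguable. One-sided exact, mid-P and Jeffreys limits all fall below 5% and 2.8%, so the claim that those rates cannot be excluded belongs to two-sided exact or Wilson limits. The plan does specify "the two-sided confidence interval for a single proportion", and the one-sided limits still exceed 3% and 2.1%.
- For 0 events in 100, the two-sided exact limit is 3.6%, but the one-sided limit is 2.95%, within the stated 3%.
- The 63% coverage comes almost entirely from samples with 0 events (0.99^100 = 36.6%), for which the plan states no limit. It illustrates the formula's failure; the tail probabilities in step 4 are the more direct evidence.
- Asking for intervals in the report goes beyond this defect and is optional.

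**Conclusion.** The concern holds. At the plan's own inputs, the stated upper limits of 3% and 2.1% should be about 5.4% and 2.9% with a two-sided 95% exact interval. The discrepancy is larger for the 12-month target. That the stated limits are too low does not depend on the method: each small-count alternative tabulated exceeds them. The exact size does depend on it, ranging from 4.58% to 5.45% for 1/100 and from 2.56% to 2.90% for 3/300.

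The assumptions are the plan's own: exactly 1% observed, 100 and 300 evaluable subjects, and independent binomial counts. The finding concerns stated precision only. It does not show that 600 enrolled, or 300 and 100 retained, is too few.

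**What to change.** In SAP 6.3, Protocol 17.1 and the protocol synopsis, replace the large-sample formula with exact (Clopper-Pearson) two-sided 95% limits. State that an observed 1% in 100 subjects excludes rates above about 5.4%, and an observed 1% in 300 excludes rates above about 2.9%. Keep the 600, 300 and 100 targets. With enrolment complete, SAP 6.3 and the precision wording in the study report are where the correction has most effect.

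Optionally, name the same exact method in the SAP for any interval reported on an AE proportion, so that the large-sample formula is not carried over to rare or zero counts.

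The cost is wording only. No subjects, visits or required analyses are added, and the stated precision becomes less favourable.

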17.2 Endpoints

17.2.1 Safety Endpoints

Safety endpoints will include:

- Incidence of any local and systemic treatment emergent AEs (TEAEs).
- Number of subjects with presence (and severity) of each individual LSR (telangiectasia, skin atrophy, striae rubrae, erythema, edema, scaling/dryness, stinging/burning, and pruritus) for each treatment area, as applicable, at each time point collected (Baseline, and LTF-Months 1, 3, 6, and 9, and any Unscheduled Visits).
- UPT results in all WOCBP at Baseline, LTF-Month 6, and EOS.

17.2.2 Efficacy Endpoints

Efficacy Endpoints will include:

- Number of subjects with each IGA severity score for each treatment area, as applicable, at each time point collected (Baseline and LTF-Months 1, 3, 6, and 9).

17.3 Statistical Methods

All statistical processing will be performed using SAS[®] unless otherwise stated. Summary tables (descriptive statistics and/or frequency tables) will be provided for baseline variables, efficacy variables, and safety variables. Continuous variables will be described by descriptive statistics (n, mean, standard deviation, CV%, minimum, median, and

maximum). Frequency counts and percentage of subjects within each category are provided for categorical data.

Subjects who complete 6 months or 12 months on-study without material non-compliance with test article (CB-03-01 cream, 1%) dosing per protocol will count towards the desired 300 subjects at 6 months and 100 subjects at 12 months. The Safety set will include all subjects who received at least one application of the test article. The intent-to-treat (ITT) set will include all enrolled subjects. The per-protocol (PP) set will be a subset of the ITT set and will include subjects who completed the study without any significant protocol deviations. The analysis of safety will be conducted on the Safety set. The analysis of efficacy will be conducted on both the ITT and PP sets.

17.3.1 Safety Analyses

Extent of Exposure

Descriptive statistics will be used to summarize exposure to test article for the Safety, ITT, and PP sets. The total amount of test article used (grams applied) will be calculated for each subject from the weights of the returned test articles. The mean daily amount of test article applied (total amount of test article used/number of days of treatment) will be calculated for each subject. The number of applications and days dosed for each treatment area (face and/or trunk from Subject Diary) will also be summarized.

Local Skin Reactions (LSRs)

LSRs (telangiectasia, skin atrophy, striae rubrae, erythema, edema, scaling/dryness, stinging/burning, and pruritus) will be summarized by the frequency of each individual LSR and severity at each clinic visit for face and trunk, separately.

Adverse Events (AEs)

AEs will be coded using the MedDRA coding dictionary summarized by relationship to test article and severity.

17.3.2 Efficacy Analyses

Investigator's Global Assessment (IGA)

Frequency distributions of IGA scores will be summarized at Baseline (EOS-Pivotal), and LTF Months 1, 3, 6, and 9 for face and trunk, separately.

17.4 Subgroup Analyses

No subgroup analyses are planned.

17.5 Interim Analyses

No interim analysis is planned.

18. ETHICAL AND REGULATORY CONSIDERATIONS

18.1 Compliance with Good Clinical Research Practice

This study will be conducted in compliance with the principles of the Declaration of Helsinki, with the current Good Clinical Practice (GCP) guidelines and with other applicable regulations. The investigator and all study staff will conduct the study in compliance with this protocol. The protocol, informed consent/assent documents, recruitment advertisements and any amendments to these items will have IRB approval prior to study initiation. Voluntary informed consent/assent will be given by every subject and the subject's parent/guardian prior to the initiation of any study-related procedures. The rights, safety, and well-being of the study subjects are the most important considerations and prevail over the interests of science and society. All personnel involved in the conduct of this study must be qualified by education, training, and experience to perform their assigned responsibilities.

18.2 Institutional Review Board (IRB)/ Ethics Committee and Informed Consent/Assent

Before study initiation, the investigator must have written and dated approval from the IRB for the protocol, consent/assent form, subject recruitment materials/process (e.g., advertisements), and any other written information to be provided to subjects and the subject's parent/guardian. The investigator should also provide the IRB with a copy of the product labeling, information to be provided to subjects/care givers, and any updates. The investigator will submit documentation of the IRB approval to the CRO.

The IRB approved consent/assent form must include all elements required by FDA (or other national health authority), state, and local country regulations, and may include appropriate additional elements.

The investigator/designee will explain the study to each potential subject and the subject's parent/guardian. The subject must indicate voluntary consent/assent by signing and dating the approved informed consent/assent form. The parent or legal guardian must provide written informed consent for the subject. The investigator must provide the subject with a copy of the consent/assent form, in a language the subject understands.

The investigator will maintain documentation that informed consent/assent was obtained prior to the initiation of any study-specific procedures.

18.3 Protocol Compliance

The IRB approved protocol must be followed except in the case of a change that is intended to eliminate an immediate risk to subjects. All protocol deviations must be documented.

18.4 Protocol Revisions

The CRO must prepare all protocol revisions. All protocol amendments must receive IRB approval prior to implementation. All administrative letters must be submitted to the IRB for their information. Copies of all correspondence with the IRB regarding this study must be sent to the CRO.

New or altered consent/assent forms required by the IRB due to a protocol change must be signed by all subjects and the subject's parent/guardian currently enrolled in the study and must be used for any subsequent subject enrollment.

18.5 Study Monitoring

Representatives of the CRO and/or the Sponsor must be allowed to visit all study sites, to review study records, and to directly compare them with source documents (including, but not limited to patient and hospital records), to discuss the study conduct with the investigator and study staff, and to verify that the investigator, study staff, and facilities remain acceptable for the conduct of the study.

Representatives of government regulatory authorities may also evaluate the study records, source documents, investigator, study staff, and facilities.

The investigator should immediately notify the CRO of any audits of this study by any regulatory agency and must promptly provide copies of any audit reports.

18.6 Case Report Form (CRF) Requirements: Electronic Data Capture (EDC)

The study will utilize validated 21CFR Part 11 compliant EDC software to collect CRF data. All requested information must be entered on the CRFs in the areas provided in a timely manner. When changes or corrections are made in the CRF, the EDC system will maintain a complete audit trail of the person making the changes, the date and time of the change, and the reason for the change. Only individuals listed on the Delegation of Responsibilities Log with responsibility for CRF completion may make entries on the CRFs. Usernames and passwords will be provided to each authorized user to allow access to the training module. Access to additional features and functions will not be enabled until the user has successfully completed the training.

The investigator or physician sub-investigator must electronically sign and date each subject's CRF. Individuals who will be providing electronic signatures must first submit documentation with a handwritten signature acknowledging that their electronic signature is a legally binding equivalent to their handwritten signature.

18.7 Reports to Institutional Review Board

The investigator should provide the IRB with reports, updates, and other information (e.g., safety updates, protocol amendments, and administrative letters) according to regulatory requirements or Institution procedures.

18.8 Quality Assurance Audits

Representatives from the CRO and/or the Sponsor or a third party selected by the Sponsor may conduct a quality assurance (QA) audit of this study. During the audit, the investigator must provide the auditor with direct access to all relevant documents and discuss any findings with the auditor.

In the event of an inspection by the FDA or other national health or regulatory authorities, the investigator must give the inspector direct access to relevant documents and to discuss any findings with the inspector. The investigator must notify the CRO in the event of a FDA or other national health authority site audit.

18.9 Records Retention

The investigator must maintain all study records (including test article disposition, informed consents/assents, CRFs and data clarification forms, if paper CRFs, source documents, correspondence, regulatory documents, contracts, etc.) for the maximum period required by the CRO or the institution where the study is conducted, whichever is longer. The Study Medication Accountability Logs will be collected at the end of the study and kept with the study records at the sites.

The investigator must contact the CRO or the Sponsor prior to destroying any records associated with this study.

If the investigator withdraws from the study, the records shall be transferred to a mutually agreed upon designee. Written notification of such a transfer must be given to the CRO.

18.10 Record Confidentiality

All laboratory specimens, evaluation forms, reports, and other records will be identified in a manner designed to maintain subject confidentiality. All records will be kept in a secure storage area with limited access. Clinical information will not be released without the written permission of the subject or the subject's parent/guardian (if appropriate), except as necessary for monitoring by the CRO or the Sponsor, the FDA or other national health or regulatory authority, or the IRB.

The investigator and all employees and coworkers involved with this study shall not disclose or use for any purpose other than performance of the study, any data, records, or other unpublished, confidential information disclosed to those individuals for the purpose

of the study. Prior written agreement from the CRO or the Sponsor must be obtained for the disclosure of any said confidential information to other parties.

